## 6.0 STUDY DESIGN AND DESCRIPTION

### 6.1 Study Design

This is a randomized, placebo-controlled, multiple-ascending dose study to investigate the safety, tolerability, PK and PD of SC administration of HM15211, conducted in 1 part.

[figure not shown]
This study will be single-blind and conducted in up to 6 cohorts comprising a total of up to 72 obese subjects with NAFLD. Each cohort will enroll subjects to ensure that at least 12 subjects per cohort will complete the study. Subjects will be randomized to investigational product (IP) or placebo in a 3:1 ratio via an Interactive Web Response System (IWRS). Per cohort (n=12 subjects), 9 subjects will be randomized to IP and 3 subjects to placebo. Cohorts may partially overlap after at least 9 subjects have completed 2-4 weeks of treatment (2 weeks of treatment is reached at Visit week 3) and a dose escalation decision has been made. Study drug will be administered weekly over a period of 12 weeks.

Based on available safety, tolerability, and PK data of each cohort, and following a safety review and dose escalation meeting between the investigator and the sponsor, dose escalation to the next cohort may proceed. Cohorts will start in sequential order but may overlap partially during execution. Replacement of dropouts and withdrawals may take place.

[figure not shown]
Each subject will undergo a screening visit, 2 in-house/ treatment periods and multiple outpatient visits. A final follow-up visit that will conclude subject study participation.

The duration of participation in this study including Screening, Treatment and Follow-up will be approximately 23 weeks for each subject including 12 weeks of treatment period.

**Figure 6-1 Study Design Schematic Cohorts 1-1 to 1-3**

**Figure 6-2 Study Design Schematic Cohort 1-4 and up**

\*Day 82 is optional for subjects in cohort 1-3

## 6.2 Study Description

Each subject will undergo the following procedures during the study:

### Screening Visit:

Before the screening takes place, potential subjects for the trial will be provided with written and oral information about the trial and the procedures involved. Subjects must sign the informed consent form (ICF) prior to entering the study. Please see section [9.1.1](#) for further details.

The screening visit will be performed up to 44 days prior to the first dosing day, to identify eligible subjects for the study. All assessments performed at the screening visit are stated in [Table 16-1](#) and will be recorded in the electronic case report form (eCRF). Please see section [9.1.2](#) and [11.2](#) for further details.

Subjects' screening lab parameters and VCTE (CAP) scores will be evaluated to identify subjects who are likely to have a liver fat content of > 10% at MRI-PDFF. Depending on the outcome/results of these values, the subjects will proceed to MRI/MRI-PDFF. For further details on parameters and outcome for the determination to proceed to MRI/MRI-PDFF see the Operations Manual. Subjects who are not able to proceed to MRI-PDFF will be recorded as screening failures.

### In-house Period 1:

Day -2: Subjects will check in to the clinic in the morning of Day -2 for a 10-day in-house period. They will receive standardized meals throughout their in-house stay. A 12-lead standard ECG will be performed. Subjects will be connected to an ABPM system for measurement of blood pressure (BP), and measurements will be started overnight on Day -2 to familiarize the subjects with the device. Measurements will continue until the morning of Day 5.

Day -1: In the morning of Day -1, subjects will get connected to a Holter ECG for continued measurement of the heart rate activity until the morning of Day 5.

Only 24-hour monitoring data from Day -1 to Day 1 will be used for the monitoring evaluation as baseline assessments for ABPM and Holter ECG monitoring. For measuring timepoints, please see sections [9.1.14](#) and [9.1.15](#).

Subjects will be randomized to weekly SC injections of HM15211 or placebo. Randomization will take place as close to the drug administration as possible.

Day 1: On Day 1, after an  $\geq 10$  h overnight fast, subjects will be dosed with HM15211 or placebo at approximately 08:00 hours (t=0), through SC injection into the abdominal wall by qualified study staff. Measurements of vital signs, blood sampling for PK at pre-dose and 8 hours after dosing and sampling for laboratory parameters including incretins/metabolic hormones, lipid profiles and particles, amino acid panel, bone metabolism parameters, glucose metabolism parameters, ketone bodies, local injection site evaluation, and evaluations for safety parameters will be performed, at timepoints stated in [Table 16-1](#).

ABPM and Holter ECG monitoring will be continued until the morning of Day 5 for the post-dose evaluation.

Subjects will continue to stay in-house for safety evaluations, PK and PD assessments as stated in the SOE. They will be released from the CRU in the morning of Day 8, after the second dose of the weekly study drug is administered. They will return for multiple outpatient visits.

#### Outpatient Visits:

Subjects will return to the CRU every week (Days 10, 15, 22, 29, 36, 43, 50, 57, 64, 71) in order to undergo assessments as described in [Table 16-1](#). Subjects will receive the injection of the study drug in an outpatient fashion to ensure compliance on Days 15, 22, 29, 36, 43, 50, 57, 64 and 71.

MRI/MRI-PDFF: Subjects will undergo an MRI-PDFF assessment during week 8, as close as possible to Day 57, but prior to the Day 57 (week 9) Dosing.

During all outpatient visits, blood samples for PK analysis, exploratory endpoints and safety assessments will be performed as stated in the [Table 16-1](#).

#### In-house Period 2:

Day 77: Subjects will check in to the clinic in the morning on Day 77 for a 5-day In-house Period. They will receive standardized meals throughout their inpatient stay. Subjects will be connected to an ABPM system, and overnight measurements will be taken to familiarize the subjects with the device. ABPM measurements will continue throughout Day 82.

Day 78 to 82: In the morning of Day 78, subjects will get connected to a Holter ECG for 24-hour measurements and will continue these until Day 82. Sample for the assessment

of PK will be collected pre-dose for  $PK_{trough}$ . Study drug will be administered. Measurements of vital signs, sampling for PK, sampling for laboratory parameters and evaluations for safety parameters will be performed as stated in the SOE

Subjects will continue to stay in-house for safety evaluations and PK. They will be disconnected from Holter monitoring and ABPM on Day 82 and will be released home in the morning of Day 82, after the PK sample has been collected.

For subjects participating in cohort 1-3, the in-house stay until day 82 is optional. These subjects will continue to stay in-house for safety evaluations, PD and PK until Day 81, after they are disconnected from Holter monitoring and ABPM.

Subjects will undergo an MRI/MRI-PDFF assessment to assess liver fat during week 12, as close as possible to Day 85. For subjects in cohort 1-5 and up, visceral fat will be assessed additionally during the imaging procedure.

Outpatient Visits:

Subjects will return to the CRU during elimination phase of the drug on Days 85 and 99. On Day 85, measurements of vital signs, sampling for laboratory parameters including incretins/metabolic hormones, lipid profiles and particles, amino acid panel, bone metabolism parameters, glucose metabolism parameters, inflammatory markers, ketone bodies, local injection site evaluation, and evaluations for safety parameters will be performed for the assessment after 12 weeks of dosing. For subjects in cohort 1-4 and up, a FibroScan assessment will be performed additionally, as stated in the SOE.

On Day 99, sampling for PK, PD and safety will be performed as stated in the SOE.

Follow-up Visit:

A Follow-up Visit will be performed on Day 113 ( $\pm 2$ ) to collect final safety assessments and the last PK sample. Please see [Table 16-1](#) Schedule of Events for details.

Sampling and Assessment:

Time points for study procedures and sample collection are specified in the [Table 16-1](#).

Safety assessments will occur throughout the duration of the study, including monitoring of adverse events (AEs), clinical laboratory tests (eg, chemistry, hematology, coagulation, amylase, lipase and urinalysis), vital signs measurements (blood pressure, heart rate, respiration rate, and aural/oral temperature), 12-lead electrocardiograms (ECGs), ABPM, Holter ECG monitoring, and physical examinations.

Local tolerability assessments will be performed by injection site inspection at specific time-points as stated in the [Table 16-1](#).

Immunogenicity samples for assessment of ADAbs, nAbs and anti-PEG will be taken prior to first dosing on Day 1, on Days 22, 50, 78, 85 and 99 as stated in the [Table 16-1](#).

The PK samples will be taken in accordance with the PK sampling schedule in section [9.1.16](#). Sampling may be adjusted based on the results of the SDRM.

The PD samples will be taken in accordance with the PD sampling schedule in section [9.1.17](#). Sampling time points may be adjusted based on the results of the SDRM.

**Follow-up Visit:**

A follow-up visit will take place on Day 113 ( $\pm 2$ ) in order to collect final safety assessments and the last PK sample.

**6.3 Rationale for Study Design and Endpoints**

This MAD study will assess the safety and tolerability, PK and PD of HM15211 in obese subjects with NAFLD compared to placebo.

Cohorts will be assessed in ascending order, but may overlap, to determine a clinically appropriate dose for the subjects and will include the comparison with placebo.

Randomization is used to avoid bias introduced through an association between study drug allocation order and subject characteristics.

A single-blind design has been chosen to avoid bias and to maintain the blind between the administration of the study drug and placebo for subjects and clinical staff.

Obese subjects with NAFLD will participate in the study, as these subjects are an important target population for the novel triple agonist. Enrollment criteria will favor the target population. Liver fat will be determined by MRI-PDFF and body mass index of  $\geq 30 \text{ kg/m}^2$ .

Measurements for the assessment of cardiovascular events will start right after dosing and will continue until Day 5.

The proposed PK endpoints are well-established, commonly used parameters to characterize pharmacological profiles of drugs. For the PK endpoints, blood samples for determination of HM15211 will be analyzed using a validated assay.

This is an exploratory study. No formal sample size calculation and no statistical hypothesis testing will be performed.

**6.4 Study Discontinuation and Stopping Criteria**

**6.4.1 Dose Escalation Criteria**

Dose decision algorithms:

- The primary tolerability criterion for decision-making will be emesis/vomiting (= GI tolerability).
- As emesis has been shown to be associated with pharmacological doses of GLP-1 agonists and glucagon, the severity of emesis is defined as follows for this study:

- Moderate: 3 to 5 episodes in 24 hours (individual episodes separated by at least 5 min)
- Severe:  $\geq 6$  episodes in 24 hours (individual episodes separated by at least 5 min) or requiring iv fluids

#### **6.4.2 Dose Escalation Stopping Criteria**

Dose escalation will be stopped if one of the following conditions apply:

- 50% or more of the subjects in the cohort have experienced moderate or severe emesis;
- 25% or more of the subjects in the cohort have experienced severe emesis;
- Death of a subject in one cohort, at any time, that is considered related to the IP, judged by the Investigator;
- One (1) or more of the subjects in a cohort have experienced a serious adverse event (SAE), that is considered related to the IP, judged by the Investigator, following discussion with the medical monitor and breaking the blind;
- Two (2) or more of the subjects in a cohort have experienced severe or medically significant adverse events (eg, common terminology criteria for adverse events [CTCAE]  $\geq$  grade 3 may be used as a grading scale at the discretion of Investigator), that is considered related to the IP, judged by the Investigator;
- Two (2) or more of the subjects in a cohort have experienced moderate adverse events for more than 7 days (eg, common terminology criteria for adverse events [CTCAE]  $\geq$  grade 2 may be used as a grading scale at the discretion of Investigator), that is considered related to the IP, judged by the Investigator;
- Two (2) or more subjects receiving HM15211 develop similar clinically significant laboratory, significant ECG or vital signs abnormalities, or severe AEs in the same organ class, indicating dose-limiting intolerance. Dose escalation may proceed if after review of the data by the Investigator and discussion with Sponsor, it is concluded that the events are not drug related;
- It is determined that the limit of safety and/or tolerability has been reached. Decision will be made between Sponsor and the Coordinating Investigator.
- All dose escalation and stopping decisions will be made following a discussion between the Coordinating Investigator and Sponsor.

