#### **10.2 Severity of AEs**

The different categories of intensity (severity) are characterized as follows:

|           |   |
|-----------|---|
| Mild:     | The event is transient, easily tolerated by the subject and does not affect the subject's daily activities. |
| Moderate: | The event causes the subject discomfort and interrupts the subject's usual daily activities.                |
| Severe:   | The event is incapacitating and causes considerable interference with the subject's usual activities.       |

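### Does the two-subject severe-AE rule in Protocol section 6.4.2 undercut the 25% severe-emesis limit in the same list?

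*Protocol*

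**What the plan says.** Section 6.4.2 opens with "Dose escalation will be stopped if one of the following conditions apply", so the conditions are alternatives. Three of them can be reached by severe vomiting:

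- The emesis limit: "25% or more of the subjects in the cohort have experienced severe emesis". It has no causality condition and its denominator is the whole cohort.
- The general limit: "Two (2) or more of the subjects in a cohort have experienced severe or medically significant adverse events", provided the Investigator judges them related to the investigational product. CTCAE grade 3 or above "may be used as a grading scale at the discretion of Investigator". Emesis is not excepted.
- The same-organ-class limit, for two or more HM15211 recipients with, among other things, "severe AEs in the same organ class, indicating dose-limiting intolerance". Escalation may still proceed if the events are concluded not to be drug related.

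A further condition halts at 50% of the cohort with moderate or severe emesis. All decisions follow discussion between the Coordinating Investigator and the Sponsor.

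Section 6.4.1 makes vomiting the primary tolerability criterion and says "the severity of emesis is defined as follows for this study", by episode count or need for intravenous fluids. Section 10.2 has the generic AE scale, where severe means "The event is incapacitating and causes considerable interference with" usual activities. Appendix B, section 4, has a separate G1 to G4 grading for managing gastrointestinal events.

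**The concern.** A limit written specifically for the primary tolerability criterion should normally be the one that governs it. Here a generic rule can act first, at two subjects instead of three. Causality will seldom hold it back. Section 6.4.1 treats vomiting as a class effect, Appendix B calls it anticipated, and section 10.3 counts a known class reaction with plausible timing as related and records unassessable cases as related too. The 25% figure could then mislead a reader about when escalation stops, and a dose-review meeting facing two severe cases might dispute which bullet was meant to apply. Several severity scales could also be brought to the same case, so the choice of scale might settle whether a second case counts. At stake is whether escalation halts at a dose where the emesis-specific rule alone would have let it continue.

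**Working it through.** **The plan's own figure.** The emesis limit needs the smallest whole number r with r/n ≥ 0.25.

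| Subjects n | Emesis limit | General limit |
|---|---|---|
| 9 (minimum at review) | 3 (33.3%) | 2 (22.2%) |
| 12 (planned cohort) | 3 (25.0%) | 2 (16.7%) |
| 13 to 16 (if dropouts are replaced) | 4 (25% to 31%) | 2 (12.5% to 15.4%) |

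So the overlap exists. At n = 12 the general limit changes the outcome in one configuration only: exactly two severe cases, both judged related. With three or more cases the emesis limit is met in any event.

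**How often that happens.** Inputs: 9 active subjects per cohort (section 6.1), no severe emesis on placebo (assumption), true severe-emesis rate p and probability r that a case is judged related (both assumed, because the protocol states neither). Let X ~ Binomial(9, p).

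- General limit alone: P(X = 2) × r².
- Any severe-emesis stop: P(X = 2) × r² + P(X ≥ 3).
- Emesis limit without the general limit: P(X ≥ 3 and at most one case related).

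| p | 0.05 | 0.10 | 0.20 | 0.25 |
|---|---|---|---|---|
| P(X = 2) | 0.063 | 0.172 | 0.302 | 0.300 |
| P(X ≥ 3) | 0.008 | 0.053 | 0.262 | 0.399 |
| General limit alone, r = 1 | 0.063 | 0.172 | 0.302 | 0.300 |
| General limit alone, r = 0.8 | 0.040 | 0.110 | 0.193 | 0.192 |
| General limit alone, r = 0.5 | 0.016 | 0.043 | 0.076 | 0.075 |
| Its share of stops, r = 1 | 88% | 76% | 54% | 43% |
| Its share of stops, r = 0.8 | 83% | 68% | 42% | 32% |
| Its share of stops, r = 0.5 | 65% | 45% | 22% | 16% |
| Emesis limit without general, share, r = 1 | 0% | 0% | 0% | 0% |
| Same, r = 0.8 | 2% | 3% | 4% | 5% |
| Same, r = 0.5 | 17% | 26% | 33% | 34% |

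Worked example, p = 0.10 and r = 0.8: 0.172 × 0.64 = 0.110; 0.110 + 0.053 = 0.163; 0.110/0.163 = 68%.

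The general limit decides more than half of the stops in 6 of the 12 cells. At p = 0.20 and 0.25, where stopping is most likely, it does so in one of six.

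**The 50% condition.** This table leaves out the moderate-or-severe emesis rule. In a cohort of 12 that rule needs 6 subjects, so two severe cases plus four moderate ones meet it. Among the seven other active subjects, P(Binomial(7, m) ≥ 4) is about 0.003, 0.13 and 0.50 for assumed moderate-emesis rates m of 0.1, 0.3 and 0.5. Those cohorts would stop on an emesis-specific rule anyway, so the general limit's added effect is somewhat smaller than shown.

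**Severity scales.** Section 6.4.1 is specific to emesis, is stated to hold for the study, and stands immediately before the stopping rules. Section 10.2 is generic. CTCAE is optional. Appendix B describes its procedures as suggestions to be tailored to the patient, and section 6.4.2 does not refer to it. A case needing intravenous fluids is severe under 6.4.1. Appendix B G3 spans moderate to severe and lists intravenous fluid, so that case fits both.

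**The case for a change.** The best argument for a change is that causality is close to automatic for vomiting on this drug class. Given three severe cases, the general limit has already been met with probability 3q²(1 − q) + q³, where q is the chance that each is judged related: 0.500 at q = 0.5, 0.896 at 0.8, 0.972 at 0.9 and 1 at q = 1. If q is high, the emesis limit almost never acts by itself. Clinical staff are blinded (section 8.6), so allocation will not ordinarily inform the causality call. The scale an Investigator picks could also settle a two-case cohort, and the repair would cost only wording.

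Much of this stands. The overlap is real, and if nearly all cases are judged related the general limit is the tighter one. It is also fair that section 6.4.2 does not say outright whether the 6.4.1 definition carries over to the general limit.

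It does not show a fault. Overlapping triggers are normal in a list where any one suffices. The emesis limit is free of the causality judgement and includes placebo subjects, so it is a count-based backstop beside a judgement-based rule. The general limit has work of its own: it counts subjects across event types, so one severe vomiting case and one severe event of another kind, both related, also reach it. Neither rule makes the other pointless.

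**Conclusion.** No change to the plan is needed. Read literally, section 6.4.2 gives one answer for two related severe-emesis cases: escalation stops. That answer errs towards caution, contradicts nothing else in the section and leaves no safeguard missing.

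In a cohort of 12 the overlap matters only at exactly two related severe cases, with probability 0.02 to 0.30 over the assumed rates (p from 0.05 to 0.25, r from 0.5 to 1, 9 active subjects, none on placebo). It would matter over a slightly wider range, two or three cases, if replacements took a cohort to 13 to 16. How often the general limit is the deciding one depends wholly on rates the protocol does not supply, so a claim that it usually pre-empts the emesis limit is not supported.

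What remains is small: whether section 6.4.1, section 10.2 or CTCAE grades vomiting under the general limit. The study-specific definition is the natural reading, and the Coordinating Investigator and Sponsor discuss every stopping decision. A confirming sentence would only record an intention. No view is taken here on which threshold or scale is clinically right.

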#### **6.4.3 Criteria for Early Termination of the Study**

The study will be completed as planned unless one or more of the following criteria are satisfied

- Violation of Good Clinical Practice (GCP) that compromises the ability to achieve the primary study objectives or compromises subject safety.
- Failure to meet expected enrollment goals
- Administrative Reasons

In case that the Sponsor, an institutional review board (IRB)/ independent ethics committee (IEC), or regulatory authority elects to terminate or suspend the study or the participation of an investigational site, a study-specific procedure for early termination or suspension will be provided by the Sponsor; the procedure will be followed by applicable investigational sites during the course of termination or study suspension.

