**Table 4-1 Treatment Allocation and Dose Escalation (NAFLD)**

| Cohorts           | Number of Subjects | Treatment Period   |
|-------------------|--------------------|--------------------|
| Cohort 1-1 | N=9                | HM15211 0.01 mg/kg |
|                   | N=3                | Matching Placebo   |
| Cohort 1-2 | N=9                | HM15211 0.02 mg/kg |
|                   | N=3                | Matching Placebo   |
| Cohort 1-3 | N=9                | HM15211 0.04 mg/kg |
|                   | N=3                | Matching Placebo   |
| Cohort 1-4 | N=9                | HM15211 0.06 mg/kg |
|                   | N=3                | Matching Placebo   |
| Cohort 1-5 | N=9                | HM15211 X mg/kg    |
|                   | N=3                | Matching Placebo   |
| Cohort 1-6 | N=9                | HM15211 0.12 mg/kg |
|                   | N=3                | Matching Placebo   |

Additional cohorts may be added if necessary, to provide sufficient data. Proposed doses for cohort 1-2 and 1-3 and 1-4 may be adjusted but will not exceed the doses stated in the table.

[figure not shown]
Each subject will be randomized to HM15211 or placebo according to the table above. The dose for the weekly dosing in cohort 1-1 will be 0.01 mg/kg, based on the body weight measured prior to the first dosing on Day -1. For dose calculation and rounding, please refer to the Operations Manual/Pharmacy Manual.

After at least  $\frac{3}{4}$  (n=9) of the subjects participating in one cohort have completed 2-4 weeks of treatment (2 weeks of treatment is reached at Visit week 3), an interim data review meeting will be held which may include a dose escalation decision. Safety and available blinded PK and/or PD data will be reviewed, and predictions based on results

from the previous study and PK/PD data modelling will be used for a dose decision/ dose escalation decision for the subsequent cohort. The dose decision will be made by the Sponsor, medical monitor and the coordinating Principal Investigator. Dose escalation will not exceed a 2-fold increase. If there are no safety concerns, the next cohort may start and may partially overlap with the previous one. An additional data review meeting may be held at the end of the completed cohort. The maximum dose for cohort 1-3 will not exceed 0.04 mg/kg. The dose for cohort 1-4 will be 0.06 mg/kg. The maximum dose for the study will not exceed 0.12 mg/kg.

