Following the dose escalation decision, the procedures for the subsequent cohorts will be identical to those described above. Therefore, all cohorts could be performed in parallel. The blind of the study will be maintained throughout. If dose escalation is stopped, dose de-escalation may occur for additional cohorts, to further refine the dose.

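### The section 6.4.2 triggers only stop escalation and the section 6.4.3 list has no drug-safety ground, so at the top dose, or with a higher cohort already dosing, no cohort-level dosing hold is stated

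*Protocol*

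**What the plan says.** Section 6.4.2 of the Protocol opens with "Dose escalation will be stopped if one of the following conditions apply". Eight criteria follow:

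- two on emesis
- a related death ("Death of a subject in one cohort, at any time, that is considered related to the IP")
- a related SAE in one or more subjects
- severe related events in two or more subjects
- prolonged moderate related events in two or more subjects
- similar laboratory, ECG, vital-sign or organ-class findings in two or more subjects
- a general judgement that the limit of safety or tolerability has been reached

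The SAE criterion is judged "following discussion with the medical monitor and breaking the blind"; the death criterion does not mention unblinding. A ninth bullet is procedural and sends escalation and stopping decisions to the Coordinating Investigator and the Sponsor.

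Section 6.4.3 says "The study will be completed as planned unless one or more of the following criteria are satisfied" and names a GCP violation, failed enrolment and administrative reasons. Its next paragraph covers the case where the Sponsor, an IRB/IEC or a regulator "elects to terminate or suspend the study or the participation of an investigational site", with a procedure to be supplied by the Sponsor.

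Section 4.5 sets the ceiling ("The maximum dose for the study will not exceed 0.12 mg/kg") and allows overlap: "If there are no safety concerns, the next cohort may start and may partially overlap with the previous one". If escalation is stopped, "dose de-escalation may occur for additional cohorts, to further refine the dose".

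**The concern.** The only stated effect of a section 6.4.2 trigger concerns the next cohort. The people at immediate risk are those already on weekly injections at the same or a higher dose. In two situations that the plan allows, stopping escalation does nothing for them:

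- The event occurs in a cohort at 0.12 mg/kg, where no escalation is left to stop.
- The event occurs in one cohort after the next, higher cohort has begun dosing.

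Section 6.4.3 is where a reader would look for the study-level consequence. Its default is completion as planned, and subject safety enters only as a result of a GCP violation. What is at stake is whether the other subjects receive their next dose while a related death or serious related event is reviewed. As written, that rests on discretion.

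**Working it through.** The plan gives no figure to reproduce. The check sets the provisions side by side and makes three simple counts.

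**1. Stated effects in section 6.4.2.** Criteria: 8. Criteria that state an effect on dosing in a running cohort: 0. All share the one lead-in sentence about escalation.

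**2. Grounds in section 6.4.3.** Listed grounds: 3 (GCP violation, enrolment, administrative). Grounds that name the drug's own safety or benefit-risk: 0.

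**3. Can the two situations arise?**

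- *Top dose.* Table 4-1 lists 0.12 mg/kg for cohort 1-6, and section 4.5 makes it the study maximum. If that cohort is opened, stopping escalation has no content. The de-escalation option concerns additional cohorts, not subjects now being dosed.
- *Overlap.* Sections 4.5 and 6.1 let the next cohort start, after a dose decision, once at least 9 subjects have completed 2 to 4 weeks. There are 12 weekly doses. At the earliest opening, subjects in the lower cohort therefore still have about 12 − 4 = 8 to 12 − 2 = 10 doses to come. The death criterion applies at any time, so a late event in the lower cohort is within its scope, but its stated effect does not reach the higher cohort.

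**4. What else could supply a hold?**

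| Provision | What it gives | Tied to a 6.4.2 trigger? |
|---|---|---|
| 6.4.3, second paragraph | Suspension or termination if the Sponsor, IRB/IEC or regulator elects it | No |
| 6.4.4 | Discontinuation of individual subjects, including at the Investigator's discretion; discontinuation of the study by the Sponsor | No |
| Appendix B | Holds for the affected subject (cardiovascular, skin, gastrointestinal, gallstone), as suggested actions | No |
| 10.4.2 | SAEs reported to the Sponsor within 24 hours | No; reporting only |
| 10.6.1 | Expedited reports on issues that could alter benefit-risk or study conduct | No; reporting only |
| 13.2 | Deviation to remove an immediate hazard | No |

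Holds for the affected subject exist, and so does a quick route to the Sponsor. No row states that the other subjects in that cohort, or in a higher one, are held pending review.

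**The case against.** The strongest reply is that the trial can be stopped and that the relevant people would know quickly. SAEs reach the Sponsor within 24 hours. Section 6.4.2 sends stopping decisions to the Coordinating Investigator and Sponsor, and its SAE criterion already involves the medical monitor and unblinding. Section 6.4.3 recognises suspension. Section 10.6.1 has a benefit-risk reporting route, and section 14.1 requires prompt reporting to the ethics board. Every dose is given by staff in the research unit, and the section 7.4 check-in criteria let the Investigator turn a subject away for a medical condition. Appendix B does state holds. All of this stands, and it limits the point to an incomplete list and an unstated link between trigger and dosing.

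A reader might infer more: that the protocol has no hold at all, or that it obliges sites to keep dosing after a related death. The documents do not support either reading. The first overlooks Appendix B and section 6.4.4; the second overlooks the suspension paragraph in section 6.4.3. Nor do they support a prediction that sites would act differently from one another, because the decision route is central.

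A second objection concerns any automatic pause. Inpatient hospitalisation makes an event serious (section 10.1.8), vomiting is anticipated (Appendix B), and an unassessable event is recorded as related (section 10.3). If every related SAE paused all cohorts at the same or a higher dose, one admission for vomiting could disturb steady-state pharmacokinetics, which is a primary objective. This also stands, and the remedy is narrowed to meet it.

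**Conclusion.** The point holds in limited form. It is a cheap improvement on patient safety. In a cohort at 0.12 mg/kg, or with a higher cohort already dosing, the protocol states no cohort-level hold for subjects other than the one affected after a section 6.4.2 trigger, and the section 6.4.3 list omits drug safety. The size is structural (0 of 8 criteria, 0 of 3 grounds); it is not an estimate of harm. Counting the doses that would fall due after an event would not measure risk either, since it assumes that nobody uses the discretion available.

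The conclusion assumes that the 0.12 mg/kg cohort is opened or that cohorts overlap; both are permitted but not certain. It does not depend on the unseen statistical analysis plan, because a rule on holding doses belongs in the protocol.

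**What to change.** **Section 6.4.3.** Add a ground to the list: *an unacceptable safety or benefit-risk finding, as judged by the Sponsor, IRB/IEC or regulatory authority*. This does not make a related death an automatic reason to terminate.

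**Section 6.4.2.** Add three elements:

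- *Pause.* Dosing and enrolment at the same or a higher dose are paused until the Sponsor and Coordinating Investigator complete a documented review. The pause applies after a death considered related to the investigational product. It also applies after a related SAE that is life-threatening or unexpected and is confirmed on unblinding to be in a subject on HM15211.
- *Unblinding after a death.* The affected subject is unblinded as part of the review, and the pause ends if that subject was on placebo.
- *All other criteria, including other related SAEs.* The existing discussion between Sponsor and Coordinating Investigator also decides and documents whether dosing continues in the affected cohort and any higher-dose cohort.

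**Missed doses.** Cross-refer to section 8.4, which already requires medical monitor approval after a dose is missed by more than one day.

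The cost is amendment wording, with no new assessments. If a pause is used, some weekly doses and steady-state PK/PD samples in the paused cohorts may be delayed or lost.
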